Initial inclusion and exclusion criteria, including medical history, ACR criteria, HADS score, and MRI safety, were established via brief phone calls. Interested individuals presented in person to the CRU to complete the remaining screening procedures. Participants underwent a urine pregnancy test and ECG. A tender point exam was administered by applying up to 4kg pressure at a rate of 1kg per second to the nineteen tender points established by the ACR³⁹ with an FPK20 manual algometer (1cm diameter; Wagner Instruments, Greenwich, CT). Thirty-three cc blood was collected by research nurses and transported to the UAB Hospital laboratory for processing and confirmation of inclusion/exclusion criteria. Participants also completed the Brief Pain Inventory (BPI)⁴² and Fibromyalgia Impact Questionnaire⁴³ (FIQ, FM participants only).

Experimental Session

Participants presented to the UAB CRU and underwent a repeat ECG for safety and were then transported to the CINL for brain imaging. Participants returned to the CRU, where endotoxin from *E. coli* (0.4ng/kg body weight, N=14, or 0.3ng/kg body weight, N=11) was administered via infusion over 30 minutes. The endotoxin dose was reduced to 0.3ng/kg after several participants experienced adverse events following 0.4ng/kg infusions. Two standardized meals of 834 kcal and 508 kcal were provided to participants prior to the first MRI session and 1 hour after the endotoxin infusion, respectively.

Image Acquisition

MRI data were collected on a Siemens Magnetom Prisma 3-Tesla scanner with 20-channel head coil. Participants laid supine, were provided with hearing protection, and were instructed to keep their eyes closed during the acquisition. A T1-weighted structural brain scan

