The Innate Central Nervous System Immune Response to an
Experimental Immune Challenge in People With Fibromyalgia

Statistical Analysis Plan

NCT04263454

Version Date: 02/16/2023

[name], Professor, Principal Investigator
University of Alabama at Birmingham
[name]

Statistical Analyses

Statistical analyses were conducted with IBM SPSS for Mac version 27. Body temperatures measured in the left and right ear were averaged for each participant. Baseline data were compared between groups using independent-samples t-tests.

Brain metabolite levels were expressed as ratios over the local CR concentration. Brain temperatures below 35.0°C and above 42.0°C were excluded as an additional data quality control measure, as temperatures outside of this range are not physiological. Mixed analyses of variance (ANOVA) were conducted with time as the within-subjects factor (levels: pre-endotoxin, post-endotoxin) and study group as the between-subject factor (levels: FM, healthy control). Endotoxin dose (0.4ng/kg vs 0.3ng/kg) and its interaction with time was added as an additional between-subjects factor, and age and the age-by-time interaction was entered as a covariate of no interest. The effects of interest were the time-by-group interaction (to test whether FM and HC participants exhibited different responses to endotoxin) and the dose-by-time interaction (to test whether participants receiving 0.3ng/kg versus 0.4ng/kg endotoxin exhibited different responses). Significant interactions were followed up with repeated-measures t-tests assessing the effect of time separately for FM patients and HCs. The dependent variables were brain temperature, CHO/CR, NAA/CR, and MI/CR in the 47 brain regions. Because of the small sample size and lack of statistical power, all tests were considered significant at $p < 0.05$. However, all tests meeting a more stringent false discovery rate threshold are highlighted. The false discovery rate threshold of 0.05 yielded a corrected p-value threshold of 0.0113.

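### The follow-up paired t-tests omit the dose and age terms of the interaction model, so the reported FM and HC changes may not decompose the interaction that was tested

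*SAP*

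**What the plan says.** The SAP (Statistical Analyses) fits a mixed ANOVA with time within subjects and study group between subjects. It states that "Endotoxin dose (0.4ng/kg vs 0.3ng/kg) and its interaction with time was added as an additional between-subjects factor" and that "age and the age-by-time interaction was entered as a covariate of no interest". The first effect of interest is "the time-by-group interaction (to test whether FM and HC participants exhibited different responses to endotoxin"; the second is the dose-by-time interaction. When an interaction is significant, the follow-up consists of "repeated-measures t-tests assessing the effect of time separately for FM patients and HCs". No dose or age adjustment is mentioned for these tests, and a paired t-test has no place for one.

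The Protocol (Experimental Session) gives the doses for both groups pooled: "0.4ng/kg body weight, N=14, or 0.3ng/kg body weight, N=11". It explains that the dose was lowered part-way through because of adverse events, and it describes no balancing of dose between FM and HC. The Participants section says that the healthy women were age-matched. Neither document gives group sizes, dose counts by group, ages by group or an estimated dose effect.

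**The concern.** The follow-up tests supply the substantive reading of a significant interaction: which group changed, in which direction and by how much. That reading can be needed for up to 4 × 47 = 188 outcomes (four measures in 47 regions).

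The interaction compares FM and HC at a common dose and age. Each raw paired change averages over whatever doses that group happened to receive. Dose followed the calendar and was not randomised, so a difference in recruitment order between FM and HC would give the groups different dose mixes. The two reported changes would then differ by something other than the effect that was tested. The SAP treats a dose-dependent response as a question of interest, so it cannot assume the dose effect away when describing each group.

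**Working it through.** The documents state no figure on this point, so there is none to reproduce.

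**Inputs from the documents.** 14 participants at 0.4 ng/kg and 11 at 0.3 ng/kg, 25 in all, an overall share at 0.4 of 14/25 = 0.56. Significance level 0.05, taken as two-sided.

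**Assumptions.** 12 FM and 13 HC; all 25 analysed in the region concerned; no group-by-dose-by-time term, since the SAP names none; dose effect on the change of 0.5 to 1 SD, where SD is the residual SD of the change score.

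**Identity.** With two time points, the interaction test is a regression of the change score (post minus pre) on group, dose and age. Least squares with a group indicator reproduces each group's mean change exactly, so:

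raw FM change − raw HC change = adjusted interaction + b_dose × (p_FM − p_HC) + b_age × (mean age FM − mean age HC),

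where p is the share at 0.4 ng/kg. The last two terms are the gap. Age-matching should keep the age term small.

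**Can the dose term vanish by design?** Equal shares would need a/n_FM = 14/25. Because 14 and 25 have no common factor, no split of all 25 gives this. The difference can still be tiny: 5/9 against 9/16 gives 0.556 − 0.563 = −0.007.

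**Size at 12 FM / 13 HC.**

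| Split at 0.4 ng/kg | p_FM − p_HC | Gap, dose effect 0.5 SD | Gap, dose effect 1 SD |
|---|---|---|---|
| 7/12 vs 7/13 | 0.583 − 0.538 = 0.045 | 0.02 SD | 0.045 SD |
| 9/12 vs 5/13 | 0.750 − 0.385 = 0.365 | 0.18 SD | 0.37 SD |

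With no dose effect the dose part is zero at any split. The arithmetic limits at these sizes are 1/12 − 13/13 = −0.92 and 12/12 − 2/13 = +0.85.

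**Check by simulation** (13 FM / 12 HC, 4,000 runs, no true group effect, dose effect 1 SD, 9/13 of FM at 0.4). The identity gives 9/13 − 5/12 = 0.276 SD. The mean raw difference was 0.27 and the mean adjusted interaction was about 0.

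**Precision of the alternative.** Ignoring age, the model-based change in group g at share 0.56 has a standard error of √(1 + n_g(p_g − 0.56)²/S) times SD/√n_g, where S = 12·p_FM(1 − p_FM) + 13·p_HC(1 − p_HC). The raw SD is inflated by √(1 + p_g(1 − p_g)·b²), where b is the dose effect in SD. Critical t is 2.201 (FM, 11 df) or 2.179 (HC, 12 df) for the raw tests and 2.080 (21 df) for the model.

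- 7/12 vs 7/13, b = 1, FM half-width in units of SD/√12: raw 1.115 × 2.201 = 2.45; model 1.0005 × 2.080 = 2.08, about 15% narrower.
- 9/12 vs 5/13, b = 1, FM: S = 2.25 + 3.08 = 5.33; raw 1.090 × 2.201 = 2.40; model 1.040 × 2.080 = 2.16, about 10% narrower.
- 12/12 vs 2/13: S = 1.69; the multiplier is √(1 + 12 × 0.44²/1.69) = 1.54 for FM and, likewise, 1.51 for HC, so model standard errors rise by 51–54%.
- 1/12 vs 13/13: S = 0.92; the same formula gives rises of 94–99%.

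**The case against.** The strongest reply is that a gap that matters needs both unequal dose shares and a dose (or age) effect on the change, and the documents show neither. The pooled counts are compatible with near-balance, and a 1 SD effect from a 0.1 ng/kg difference in dose is only an assumption. The time-by-group test is itself adjusted, the paired tests run only after a significant interaction, and each validly describes its own group. All of this stands, and it makes the point one of interpretation only.

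A reader might go further and infer that the raw tests are always less precise. The working does not support that. Model-based intervals are narrower at moderate splits if dose has a sizeable effect, but they are wider when dose and group are strongly collinear, which is where the gap can be largest. The 21 df also depend on equal error variance in FM and HC, which separate t-tests do not require.

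A reader might also infer that the raw changes could point the opposite way from the interaction. That would need a dose term of opposite sign and larger than the adjusted effect, and nothing in the documents suggests one. With a true group effect of 0.80 SD, a 1 SD dose effect and 9/13 of FM at 0.4, the simulated raw difference averaged 1.07: distorted, but with the same sign.

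The objection does not remove the mismatch. An adjusted contrast is explained by unadjusted components, and without dose counts by group the reader cannot tell whether that matters.

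**Conclusion.** The point holds in a conditional form: the two within-group changes may not decompose the tested interaction. That the follow-up omits the dose and age terms is plain from the SAP. The size is not established. Under the 12/13 assumption and the two splits shown, the dose part of the gap lies between about 0.02 and 0.37 SD of change, and it would be zero without a dose effect. Temperature values outside the SAP's accepted range are excluded, so dose shares may also vary between regions. The documents do not support a claim that the groups' dose mixes differed materially, or that any statement of which group responded is wrong. I rate this a cheap improvement.

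**What to change.** 1. Report the number of FM and HC participants at each dose, and for brain temperature the counts left after exclusions.
2. Replace the follow-up t-tests by simple effects of time in each group, as estimated marginal means with 95% CIs from the fitted model, at the same dose weights for both groups and at mean age. In SPSS this is EMMEANS with COMPARE(time). State the dose weights: with no group-by-dose-by-time term they do not alter the FM-HC difference, but they do alter each group's estimated change. The two simple effects then differ by exactly the tested interaction.
3. Keep the raw paired changes as descriptives, labelled as unadjusted.

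The cost is a few lines of syntax and one sentence in the SAP, with no new data. The SAP is written in the past tense with an FDR cut-off already obtained, so this would be a supplementary re-analysis. The report should state the downside: the model-based effects assume a common error variance in FM and HC and lose precision if dose and group are strongly collinear. The counts in step 1 will show whether they are.

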The Innate Central Nervous System Immune Response to an
Experimental Immune Challenge in People With Fibromyalgia

Protocol

NCT04263454

Version Date: 01/06/2021

[name], Professor, Principal Investigator
University of Alabama at Birmingham
[name]

Methods

Design

This study utilized a mixed (group-by-time) design to compare changes in brain metabolites before and after an experimental endotoxin challenge between FM and HC groups. Participants underwent an MRI 1.5 hours before receiving the endotoxin infusion, and 4 hours after. The following were measured with EPSI in 47 brain regions as primary outcomes: brain temperature, CHO, MI, and NAA.

Procedures

Study procedures were approved by the University of Alabama at Birmingham (UAB) Institutional Review Board and conducted in accordance with the Declaration of Helsinki. Participants provided written informed consent prior to any procedures. A payment of \$50 was provided following completion of the screening visit, and \$600 was provided for the experimental session. Screening and experimental sessions were performed at the Clinical Research Unit (CRU) located at UAB Hospital. Brain imaging was conducted at the UAB Civitan International Imaging Laboratory (CINL). During the experimental session, participants were transported between locations via rideshare transportation.

Participants

Women with FM aged 18-55 and healthy age-matched women were recruited from the Birmingham community via online advertisements on the UAB Clinical Trials website. Our laboratory maintains a database of individuals who have indicated an interest in research, from which additional participants were contacted. Participants in the FM group met the revised diagnostic criteria by the American College of Rheumatology,^{1,39,40} endorsed at least eleven out of nineteen positive tender points on a physical exam, and reported an average daily widespread

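### The SAP judges 376 interaction tests on 188 primary outcomes at uncorrected p < 0.05, citing low power; the FDR result it also computes only highlights findings and does not decide significance

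*SAP*

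**What the plan says.** The protocol (Methods, Design) states: "The following were measured with EPSI in 47 brain regions as primary outcomes: brain temperature, CHO, MI, and NAA". The SAP (Statistical Analyses) carries the same set into the models, with the metabolites as ratios to creatine: "The dependent variables were brain temperature, CHO/CR, NAA/CR, and MI/CR in the 47 brain regions". For each dependent variable it names two effects of interest. Time-by-group asks whether fibromyalgia patients and controls respond differently to endotoxin, and dose-by-time asks whether the two endotoxin doses differ.

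The significance rule is: "Because of the small sample size and lack of statistical power, all tests were considered significant at" p < 0.05. A second tier follows: "However, all tests meeting a more stringent false discovery rate threshold are highlighted". Its cut-off is then given: "The false discovery rate threshold of 0.05 yielded a corrected p-value threshold of 0.0113". Interactions that are significant are followed by within-group t-tests of the time effect, run separately in patients and controls.

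Neither document names a lead outcome, a hierarchy or a global test, and neither labels these tests exploratory. The SAP does not say which FDR procedure was used or which tests it covered.

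**The concern.** The number of false positives that a rule admits depends on the number of tests and the threshold. A small sample does not reduce it: each true null still has a 5% chance of giving p < 0.05. Low power reduces only the number of true effects found. It can be a reason to call an analysis exploratory, but it is not a reason to call uncorrected results on 188 primary outcomes significant.

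What is at stake is which regions are claimed. The same word also controls the next step, because an interaction that reaches p < 0.05 without passing FDR still qualifies for within-group t-tests. That region then acquires a patient-versus-control account. Regions within a participant are likely to be correlated, so false positives would tend to come in groups that can look like an anatomical pattern.

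**Working it through.** **Inputs.** Regions: 47 (protocol, Design; SAP). Measures: 4 (same places). Interactions of interest: 2 (SAP). Per-test threshold: 0.05 (SAP). FDR level 0.05 and resulting p threshold 0.0113 (SAP). Participants: 14 + 11 = 25 (protocol, Experimental Session). The documents give no power calculation.

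**1. The plan's own figure, 0.0113.** This threshold depends on the observed p-values, so it can be checked for consistency but not reproduced. Under the usual step-up (Benjamini-Hochberg) procedure the critical value at rank k of m tests is k x 0.05/m.
- m = 376: k = 85 gives 85 x 0.05/376 = 0.01130, a match.
- m = 188: k = 42 gives 0.0112 and k = 43 gives 0.0114. No critical value rounds to 0.0113, although an observed p of 0.0113 at rank 43 would pass.
- m = 141, 564 and 752 also have matching ranks.

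The figure is plausible, but it does not identify the family.

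**2. Number of tests.** 4 x 47 = 188 outcomes; 188 x 2 = 376 interaction tests. Baseline comparisons, main effects and follow-up t-tests are not counted.

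**3. Expected false positives under the complete null.**
- Both interactions: 376 x 0.05 = 18.8
- Time-by-group alone: 188 x 0.05 = 9.4
- One measure, one interaction: 47 x 0.05 = 2.35

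These means hold under any correlation between tests. If some effects are real, the expectation is 0.05 x (number of true nulls), which is smaller. With independent tests the standard deviation would be sqrt(376 x 0.05 x 0.95) = 4.2 and the central 95% range 11 to 27. Positive correlation widens that range.

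**4. The band between the two thresholds.** 0.05 - 0.0113 = 0.0387. Taking 0.0113 as a fixed reference point, 376 x 0.0387 = 14.6 tests would be expected there under the complete null, and 376 x 0.0113 = 4.2 below it. So 14.6 of the 18.8 would be called significant while failing the SAP's own stricter cut-off.

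**5. Effect of correlation, one measure and one interaction.** For 47 independent tests, the chance of at least one false region is 1 - 0.95^47 = 0.91. A null simulation used 25 participants, an assumed 12/13 group split, dose and age in the model (21 error degrees of freedom) and 4,000 replicates per setting. The table shows the chance of at least one false region.

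| Between-region correlation | Uncorrected p < 0.05 | Step-up FDR 0.05 |
|---|---|---|
| 0 | 91% | 5.3% |
| 0.5 | about 62% | 3.8% |
| 0.7 | about 41% | 2.5% |

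At correlation 0.5, about one null family in twenty showed 10 or more false regions. The group split and the correlations are assumptions; the documents give neither.

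**The case against.** The strongest reply is that an FDR analysis exists and its results are marked. That is right. A reader can see which results pass, so it would be wrong to infer that the study cannot tell signal from noise. The fault is narrower: the word *significant*, and the follow-up testing attached to it, sit with the uncorrected tier.

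A second reply is that 0.0113 points to many real effects. If the procedure is step-up FDR, k/m must be at least 0.0113/0.05 = 0.226, so at least 22.6% of the family passed. That does not look like a complete null. A reader might take 18.8 as the number of reported findings that are false, or suppose that most of them are. The documents support neither reading. For example, assuming 10% real effects at 20% to 45% power predicts that only 0.9 x 0.05 + 0.1 x 0.20 = 6.5% to 0.9 x 0.05 + 0.1 x 0.45 = 9% of tests fall below 0.05, far short of 22.6%. On the SAP's figure, the false share at p < 0.05 across the FDR family would be roughly 0.05/0.226 = 22% at most, subject to correlation and to the unnamed procedure and family. For the same reason, 0.0113 does not show that time-by-group in particular is non-null.

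Third, the total of 376 pools two questions, and the protocol applies the word primary to the measures, not to the tests. This is fair, which is why 9.4 is given separately for the fibromyalgia question. Finally, lenient thresholds can be defended in exploratory work. They can, if the work is labelled so; here the outcomes are called primary.

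**Conclusion.** The concern holds as a fault in the decision rule. All 376 tests on 188 primary outcomes are judged at uncorrected 0.05, and the reason given does not support that. This does not mean that all 376 came out positive. Under the complete null the rule admits 18.8 expected false positives, 9.4 of them for time-by-group, and about 14.6 of the 18.8 would fail the SAP's own FDR cut-off. The counts follow directly from the documents. The 18.8 and 9.4 need no assumption about correlation and are ceilings on the expected number. The 14.6 treats 0.0113 as fixed. The chances of at least one false region rest on the assumed split and correlations and are indicative only. How many of the reported results are false cannot be determined from the documents.

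**What to change.** In the SAP's Statistical Analyses section:

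1. Make the FDR-adjusted result the criterion for calling a test significant and for going on to the within-group t-tests. Apply it to both time-by-group and dose-by-time.
2. Name the FDR procedure and the family of tests it covers, for example a separate family of 188 for each interaction. If that differs from the family behind 0.0113, recompute the threshold.
3. Report other results with p < 0.05 as nominal and hypothesis-generating, with the estimate and 95% confidence interval, and keep them out of the conclusions.
4. Delete the sentence that gives small sample size and low power as the reason for uncorrected testing.

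This takes revised wording, relabelled tables and, at most, a recalculation from existing p-values. No new data or new endpoint is needed. The downside is that fewer regions will be labelled significant. Because the SAP already reports its FDR threshold, the revision should state that it was made after the analysis.
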